Official title: Mindfulness-Based Intervention for Caregivers of Frail older adults:
Towards a model of intergenerational caregiving for Chinese families

NCT number: to be assigned

Document date: April 22, 2021

The research questions of the proposed study are:

- 1) investigate the effects of a brief mindfulness-based intervention for caregivers of frail elders in reducing caregiver burden and depression;
- 2) compare the effects of mindfulness-based intervention with an evidence-based caregiver programme; and
- 3) explore the factors that contribute to the positive improvements of both caregiver programmes, and develop a preliminary model for understanding and reducing caregiver burden and depression.

RESEARCH PLAN AND METHODOLOGY

Study design

In view of the research objectives about efficacy of the MBI and in the interest of developing a model of mediators in the MBI and intergenerational caregiving, a multi-site, three-arm, randomized controlled trial will be implemented (Baron et al., 2013). The effects of the MBI for caregivers for frail elderly will be tested by comparing the MBI (Arm 1), with psychoeducation (Arm 2), and treatment-as-usual (Arm 3). Assessments will be scheduled pre-intervention (T0), post-intervention (T1), and at 6-month follow-up (T2). The program effects will be tested using both pairwise between-subject comparisons (Arm 1 vs Arm 2, Arm 2 vs Arm 3, and Arm 1 vs Arm 3) and within-subject comparisons (measures at T0, T1, and T2). The between-group analyses will be adjusted for baseline scores and for factors related to outcomes, including the age and sex of the caregivers, the severity of depression, anxiety, caregiver burden, and the level of frailty of elderly. Refinement of design from a pilot study. A pilot study has been conducted in August to September 2019.

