The research project will be announced and promoted among collaborating NGOs and through advertisement in social media, promotional emails, and project leaflets. Four NGOs have indicated their intentions to contribute to this study by assisting in promotion, recruitment, program implementation and data collection. Support letters of these NGO collaborators have been provided in the appendix.

We will organize briefing sessions for explaining the rationale and procedures of the study half yearly. All interested caregivers will be screened using Clinical Frailty Scale, Clinical Dementia Rating Scale, and caregiver stress. Written consent will be collected for eligible participants. All NGO collaborators will provide standard care to the participants, including participants in Arm 3 who will not receive MBI nor psychoeducation before T2. The Research Assistant who is blinded to the personal data of the participants, will administer the random assignment using computer generated programming. Participants will be randomly assigned to MBI (Arm 1), psychoeducation (Arm 2), or treatment-as-usual (Arm 3). During the recruitment and implementation, both arm 1 and 2 are called "Family Psychoeducation Program", and the term "mindfulness" will not be used for Arm 1 to minimize the potential placebo effect. Cash remuneration coupons will be provided to caregivers who can complete the study at T1 and T2. A recruitment flowchart is attached in Appendix 1.

Procedures

Program planning and training. The themes and content of arms 1 and 2 are summarized in Appendix 2.

MBI (Arm 1). Based on the protocols of PI's previous clinical trials, brief mindfulness exercises will be integrated with psychoeducation of caregiving for frail elderly. The protocol for Arm 1 has been developed on mid-Sept, 2019 for the first pilot study.

Psychoeducation.

(Arm 2). The research team will modify START (STrAtegies for RelaTives) program for

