caregivers of dementia (Livingstone et al., 2014) into a 10-hour group program. Major changes include the content originally related to the caregiving needs of dementia will changed to frail elderly. Two hours will be added to allow for more discussion of individual caregiver's concerns. The protocol for Arm 2 will be developed and a pilot study will be conducted shortly in early 2020. Arm 1 and 2 are parallel in program design. Both will be 4-session programs to be organized bi-weekly, and last for 10 hours in total. Both programs include 15-minute daily home practice assignments, with Arm 1 being guided with mindfulness exercises, and Arm 2 with coping and problem-solving skills. Both arms will be delivered in group format, with 10 to 15 caregivers in each group. Programs will be conducted in the service units of four NGO collaborators and PI's university. All instructors for Arm 1 require basic professional training in MBI, plus at least two-year experience in conducting MBI. Instructors for Arm 2 will be recruited from NGO with experience in working with caregivers of frail elderly for more than two years. Implementation and assessment.

After the pre-intervention assessment (T0), caregivers who meet inclusion criteria will be randomized into a MBI (Arm 1), psychoeducation (PSY, Arm 2), or treatment-as-usual (TAU, Arm 3). After the intervention programs, participants in three arms will complete the post-intervention assessment (T1). A 6-month follow up (T2) is offered as a booster and final assessment for arms 1 and 2. This study will be single-blinded and outcome assessors will be blinded to randomization status.

To ensure intervention fidelity, all program sessions will be audio-recorded and an independent rater will listen to 20% of the selected clips on random basis, and assess whether each element in the intervention protocol has been implemented with consistency. Higher concordance rates will signify greater fidelity to the intervention protocol, which will be carefully monitored throughout the study. The treatment fidelity of Arm 1 will be further assessed by Mindfulness-based Interventions-Teaching Assessment Criteria Scale (Crane et al., 2013). Those of Arm 2 will be assessed by a checklist for implementing START program.

Table 1. Outcome variables and measures

Study variables and measures	Validation in HK samples
Primary outcome variables	

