All analyses will be carried out according to the intention-to-treat approach and all participants who receive randomization and allocation to one of three treatment arms will be included for analyses (Moher et al., 2010). Repeated measure ANOVA will be used to evaluate the effects of the MBI (Arm 1), relative to PSY (Arm 2) and TAU (Arm 3), and the analyses of the primary and secondary outcome measures will be analyzed. In addition to the immediate programme effects, outcomes measured at T1 and T2 will be compared, to assess whether maintenance effects will be sustained at 6-months.

The mediation effects on the relationships between group (MBI or PSY vs. TAU)

variables and caregiver outcome variables (ZBI, CES-D, HAD-A), controlling the baseline variables (sex and age of caregivers, frailty score), will be evaluated using the PROCESS macro in SPSS (Hayes, 2012), in order to compute the effect of the independent variable on the mediator (a), the effect of the mediator on the dependent variable (b), total effect (c), direct effect (c'), and bootstrapped (i.e., 10,000 random samples) bias-corrected 95% confidence intervals of the indirect effect (ab).

According to Hayes (2009), with significant paths a and b, even without a significant path c, confidence intervals that do not include zero indicate a significant indirect (i.e., mediation) effect.

Appendix 1
Recruitment Flowchart

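### The plan conflicts on whether Arm 3 (usual care) is assessed at T2, and its 6-month maintenance analysis ties no between-arm contrast to T2

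*Combined protocol and SAP*

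**What the plan says.** Four parts of the combined protocol and SAP bear on this point.

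- **Study design.** The schedule is given for the three-arm trial as a whole: "Assessments will be scheduled pre-intervention (T0), post-intervention (T1), and at 6-month follow-up (T2". Programme effects are to be tested by "pairwise between-subject comparisons (Arm 1 vs Arm 2, Arm 2 vs Arm 3, and Arm 1 vs Arm 3", with no time point named, and by "within-subject comparisons (measures at T0, T1, and T2". It adds: "The between-group analyses will be adjusted for baseline scores".
- **Recruitment of participants.** Standard care goes to everyone, "including participants in Arm 3 who will not receive MBI nor psychoeducation before T2". Coupons are offered for completing T1 and T2, with no limit by arm.
- **Implementation and assessment.** After the programmes, "participants in three arms will complete the post-intervention assessment (T1". The next sentence reads: "A 6-month follow up (T2) is offered as a booster and final assessment for arms 1 and 2".
- **3. Data Analyses.** The approach is intention-to-treat, covering everyone randomised to any of the three arms. A repeated-measures ANOVA evaluates Arm 1 relative to Arms 2 and 3, with no time points named. The one sentence on durability says that "outcomes measured at T1 and T2 will be compared, to assess whether maintenance effects will be sustained at 6-months".

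**The concern.** Two linked problems affect the 6-month result.

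First, the section that site staff would follow moves from three arms at T1 to two arms at T2 in adjacent sentences. The rest of the document reads as if all three arms are followed to T2. If sites take the narrower sentence at its word, usual care has no 6-month data and neither programme can be compared with it at that point. T2 assessments that are not done on time cannot be recovered later.

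Second, even if all arms are assessed, the maintenance sentence compares one time point with another and does not say between which arms. If it is applied within a programme arm, it answers whether scores moved after the programme ended. It does not answer whether caregivers were still better off than under usual care.

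**Working it through.** No figure in the plan is in dispute here, so there is none to reproduce. The check compares the sections and then counts what would be lost.

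**Step 1. Is Arm 3 assessed at T2?**

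- Study design: yes, by implication. T2 is scheduled with no arm excluded, and two of the listed contrasts involve Arm 3.
- Recruitment of participants: yes, by implication. Keeping Arm 3 off both programmes until T2 has little purpose unless Arm 3 is observed at T2. The T2 coupon is not limited by arm.
- Data Analyses: yes, by implication, since all three arms are in the analysis set.
- Implementation and assessment: no, if read literally. Its limit to Arms 1 and 2 grammatically covers the last assessment as well as the booster, and it follows directly on a sentence naming three arms for T1.

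No sentence states outright that Arm 3 completes T2. The conflict is therefore between one explicit sentence and several implications.

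**Step 2. Contrasts lost at T2 under the literal reading.**

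Three arms give 3 × 2 / 2 = 3 pairs, as the plan lists. Two of them (Arm 1 vs 3, Arm 2 vs 3) need Arm 3. Without Arm 3 data at T2, 3 − 2 = 1 contrast remains: Arm 1 vs Arm 2.

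**Step 3. Records lost.**

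Inputs: 240 caregivers and 15% drop-out (Sample size estimation). Equal allocation is assumed, because the plan gives no ratio.

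- Per arm randomised: 240 / 3 = 80.
- Per arm at T2: 80 × (1 − 0.15) = 68.
- T2 records with three arms: 3 × 68 = 204.
- T2 records with Arms 1 and 2 only: 2 × 68 = 136.
- Difference: 204 − 136 = 68, all from Arm 3.

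**Step 4. What a T1–T2 comparison can show.**

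Let P1 and P2 be a programme arm's mean at T1 and T2, and U1 and U2 the same for usual care. The difference from usual care is A1 = P1 − U1 at T1 and A2 = P2 − U2 at T2. Then

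A2 − A1 = (P2 − P1) − (U2 − U1).

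A within-arm comparison estimates only P2 − P1. If the programme arm is perfectly stable (P2 = P1), then A2 = A1 − (U2 − U1). The difference may be fully kept, reduced or gone, depending on a usual-care change that the within-arm comparison does not contain. Maintenance of benefit over usual care needs A2 itself, that is, a between-arm contrast at T2 or the equivalent arm-by-time contrast.

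**The case against.** The strongest reply is that this is one loosely worded sentence in a plan that otherwise points one way. Only Arms 1 and 2 have a programme to boost, so the limit to those arms may attach to the booster alone. The Appendix 1 flowchart and a figure in Data Analyses were not available for this review and may show follow-up by arm; their absence here is not a fault of the plan. This is the more coherent reading. It does not remove the need for a correction, because the sentence as written also covers the last assessment.

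On maintenance, the reply is that baseline-adjusted contrasts with Arm 3 and a three-arm repeated-measures ANOVA are already planned, and that the maintenance sentence follows directly on that model. This largely stands. A controlled 6-month comparison is a natural reading. What remains is that no sentence ties a between-arm contrast to T2, while T2 is named in Study design only in the schedule and under within-subject comparisons.

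A reader might infer more in three ways, none of which the documents support:

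- That maintenance will be judged within arm. No passage says so; the wording only leaves it open.
- That no between-arm analysis could include T2. The planned ANOVA and contrasts could include it.
- That Arm 3 would drop out of the repeated-measures analysis altogether. That depends on a complete-case analysis, which the plan does not specify; it states intention-to-treat.

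**Conclusion.** The conflict over Arm 3 at T2 is real and should be resolved. Followed literally, Implementation and assessment removes two of the three planned contrasts at 6 months and about 68 Arm 3 records, assuming equal allocation and the plan's 15% drop-out. The documents do not show that the sponsor intends this. The weight of the other sections suggests that Arm 3 is to be followed, so the finding is a contradiction with a serious consequence on one reading, not proof that the control arm is missing.

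The maintenance point is narrower. The suitable between-arm analyses are already planned, but the one sentence on maintenance does not assign them to T2. That a within-arm T1–T2 comparison cannot answer the question follows from the algebra above and needs no assumed effect size or correlation. No claim is made here about the power of the 6-month comparison.

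**What to change.** 1. In Implementation and assessment, reconcile the T2 sentence with Study design and Recruitment of participants, so that it says T2 outcomes are collected in all three arms. Describe the booster in a separate sentence, so that any limit by arm attaches to the booster alone. Check that the Appendix 1 flowchart agrees.

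2. In Data Analyses, state that the 6-month maintenance conclusion rests on the baseline-adjusted Arm 1 vs Arm 3 and Arm 2 vs Arm 3 contrasts at T2, or the equivalent arm-by-time contrast from T0 to T2 in the planned model, each with a 95% interval. Report within-arm change from T1 to T2 as supporting information.

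Cost: wording only if Arm 3 is already followed to T2, as Study design and Recruitment of participants imply. If the narrower sentence was meant literally, the change adds up to about 80 assessments (240 / 3, assuming equal allocation), with the T2 coupons that go with them. The between-arm analyses add nothing, since the contrasts and the baseline adjustment are already in the plan.

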Caregiver burden - Measured by 22-item Zarit Burden Interview (ZBI) (Zarit et al., 1980)	$\alpha = .88$ (Tang et al., 2017)
Secondary outcome variables	
Depressive symptoms - measured by 10-item The Center for Epidemiologic Studies Depression Scale (CES-D) (Radloff, 1977)	$\alpha = 0.78$ (Boey, 1999)
Anxiety symptoms - measured by 7-item Hospital Anxiety and Depression Scale – Anxiety subscale (HAD-A) (Zigmond & Snaith, 1983)	$\alpha = 0.77$ to 0.82 (Leung et al., 1999)
Positive caregiving experiences - Measured by 9-item Positive Aspects of Caregiving Scale (PAC) (Tarlow et al., 2004)	$\alpha = 0.89$ (Lou et al., 2015)
Spiritual well-being - measured by 12-item Functional Assessment of Chronic Illness Therapy–Spiritual Well-Being Scale (FACIT-Sp-12) (Peterman et al., 2002), with two subscales in meaning/peace and faith	$\alpha = 0.80$ (Wang, 2016)
Family conflicts - measured by 10-item Revised Conflict Tactics Scale (CTS2) (Beach et al., 2005), with subscales in psychological mistreatment (5 items) and physical abuse (5-items)	$\alpha = .81$ to $.82$ (Yan & Tang, 2001)
Biomarker: Heart rate variability - measured by the CorSense Heart Rate Variability monitor	N.A.
Mediators of outcome	
Cognitive factor: Coping styles - measured by 28-item brief COPE (Carver, 1997), with 11 subscales (problem-solving, accommodation, support-seeking, behavioral disengagement, denial, self-distraction, self-blame, humour, venting, substance use, and religion)	$\alpha = 0.76$ for whole scale, and $\alpha = .49$ to $.87$ for subscales (Tang et al., 2016)
Cognitive factor (psychoeducation-specific): Self efficacy - Measured by 5-item subscale of controlling upsetting thoughts (5 items) in the Revised Scale for Caregiving Self-Efficacy (RSCSE) (Steffen et al., 2002)	$\alpha = .86$ (Au et al., 2009)
Cognitive factor (mindfulness-specific): Experiential avoidance - measured by 15-item The Brief Experiential Avoidance (BEAQ) Questionnaire (Gamez et al., 2011)	$\alpha = 0.81$ (Lo et al., in review)

3. Data Analyses

[figure not shown]

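### The mediation models name only sex, age and frailty as covariates, so a mediator-outcome correlation already present at T0 can pass as mediation whenever a programme moves the mediator

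*Combined protocol and SAP*

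**What the plan says.** The mediation paragraph of Data Analyses compares MBI or psychoeducation with treatment as usual. The outcomes are ZBI, CES-D and HAD-A, and the models are fitted "controlling the baseline variables (sex and age of caregivers, frailty score), will be evaluated using the PROCESS macro in SPSS". The candidate mediators in Table 1 are the brief COPE subscales, the RSCSE self-efficacy subscale and the BEAQ. The paragraph does not mention the T0 value of the mediator or of the outcome, does not define change scores, and does not say at which visit mediator and outcome are taken.

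The decision rule is that "with significant paths a and b, even without a significant path c, confidence intervals that do not include zero indicate a significant indirect" effect.

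Study design has a broader adjustment: "The between-group analyses will be adjusted for baseline scores and for factors related to outcomes". The factors listed there include severity of depression, anxiety and burden. The sentence follows the description of the pairwise and within-subject programme comparisons and does not mention mediation.

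The mediation tests serve research question 3, which is to "explore the factors that contribute to the positive improvements of both caregiver programmes" and to build a preliminary model from them.

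**The concern.** Path b is an observational association between two questionnaire scores, even inside a randomised trial. A caregiver with high experiential avoidance at T0 is likely also to report more distress at T0, and both tend to persist to T1. A regression of the T1 outcome on the T1 mediator that omits the T0 values reads this carried-over correlation as an effect of the mediator. Sex, age and frailty score are not substitutes for the T0 scores.

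If the programme also shifts the mediator, a is significant, b is significant for the wrong reason, and the interval for ab excludes zero. The plan then declares mediation, and does so even when the programme has no detectable effect on the outcome. The model promised under research question 3 could therefore be built on mechanisms that play no causal part.

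**Working it through.** **Inputs from the documents.** Total 240, so 80 per arm if allocation is equal (assumed). Drop-out is 15%, so 80 × 0.85 = 68 per arm and 136 in a two-arm mediation model. Two-sided 5%. The plan's effect sizes give 0.64 − 0.14 = 0.50. A two-sample t-test at 80% power then needs 63.8, so 64 per arm, which reproduces the plan's figure. That 0.50 is for depression. Using it for the mediator shift is an assumption.

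**Assumed, because the documents give no values.** Mediator-outcome correlation at T0, r = 0.1 to 0.5. T0-T1 stability of each scale, s = 0.4 to 0.7. Mediator shift a = 0.5 SD, with 0.3 as a check. True b = 0.

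**Size of the spurious path.** Let M1 = s·M0 + a·group + noise and Y1 = s·Y0 + noise, with independent noise terms and unit variance within arm. The within-arm correlation of M1 and Y1 is then r·s². Without T0 values, b estimates r·s² and the spurious indirect effect is a·r·s². At s = 0.6:

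- r = 0.3: b = 0.3 × 0.36 = 0.108; ab = 0.5 × 0.108 = 0.054 SD
- r = 0.5: b = 0.5 × 0.36 = 0.180; ab = 0.5 × 0.180 = 0.090 SD

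The simulated means were 0.053 and 0.089 SD.

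**How often the rule fires, by hand.** For a: z = 0.5 × √(68 × 68/136) = 2.915, so power is about 0.83. For b: z = b × √130 / √(1 − b²), with 136 − 6 = 130 degrees of freedom.

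- r = 0.3: z = 1.24, power 0.236; joint 0.83 × 0.236 = 0.196
- r = 0.5: z = 2.09, power 0.550; joint 0.83 × 0.550 = 0.457

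**Simulation of the full rule** (2,000 trials per cell; a and b each p < 0.05 and the bias-corrected bootstrap interval excluding zero, with 500 resamples; raw T1 scores; three inert covariates standing for sex, age and frailty). False mediation with no T0 values in the model:

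| Baseline r | s = 0.4 | s = 0.5 | s = 0.6 | s = 0.7 |
|---|---|---|---|---|
| 0.1 | 4.6% | 5.3% | 6.2% | 7.0% |
| 0.3 | 5.8% | 11.2% | 18.8% | 28.6% |
| 0.5 | 10.1% | 24.5% | 43.4% | 65.4% |

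The interval requirement puts the simulated rates slightly below the hand figures. Monte Carlo standard error is about 0.5 points near 5% and 1.1 points near 50%.

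**Variations at s = 0.6 (r = 0.3 / r = 0.5).**

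| Setting | No T0 values | Both T0 values |
|---|---|---|
| Base case | 18.8% / 43.4% | 4.5% / 3.8% |
| a = 0.3 SD | 8.4% / 22.2% | |
| Change scores | 8.7% / 17.2% | |
| MBI and PSY pooled, 136 vs 68 | 30.5% / 66.2% | 4.2% / 5.0% |
| Reliability 0.81 (BEAQ) and 0.78 (CES-D), latent stability 0.75 | 26.1% / 57.6% | 4.2% / 4.9% |

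Adding the T0 outcome alone gives 3.6% / 3.6% in the base case. With the Table 1 reliabilities it leaves 6.2% / 9.2%.

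**Cross-check with another interval method.** Using a Monte Carlo interval for ab, r of 0.3 or 0.5, s of 0.5 or 0.7, and 68 or 80 per arm, the rates were 11% to 75% under the planned covariates and 4% to 6% with both T0 values. With a = 0 the planned model gave at most about 5%.

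**The case against.** The strongest reply is that Study design already covers most of this. Its baseline-score adjustment applies to between-group analyses, and the mediation paragraph describes relations between group and outcome. On that reading the T0 outcome is in the model and the excess falls to nil, or to 6-9% with measurement error. The reading is tenable, but no text carries the adjustment over to mediation, the mediation paragraph has a different and shorter list of its own, and the T0 mediator is not named there.

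Second, the score type is unstated, and research question 3 speaks of improvements, which fits change scores. Change scores roughly halve the problem (9% and 17%) but do not remove it: at s = 0.6 the two changes still correlate at (1 − s)²r / [2(1 − s)] = 0.16r / 0.8 = 0.2r.

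Third, the magnitude is all assumption. That is correct. At r = 0.1 the problem is negligible. The ZBI-4 entry threshold restricts the range of T0 burden, and some COPE subscales have a reliability as low as .49. Both would tend to weaken baseline correlations, so r = 0.5 is less plausible for burden than for depression or anxiety.

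Fourth, adjustment has limits. Confounding that arises after T0 remains. The 4-5% is per test: 13 mediator scores (11 COPE subscales, RSCSE, BEAQ) against three outcomes make 39 tests per contrast. These limits stand, and none is a reason to leave out the T0 values.

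**Conclusion.** The concern holds. As written, the covariate list leaves path b confounded by the T0 scores, under a rule that accepts mediation on a, b and the interval. The bias takes effect only when the programme moves the mediator.

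In the base case false mediation is 19% to 43% for baseline correlations of 0.3 to 0.5; across the assumed grid it is 5% to 65%. The mechanism is certain. The size depends on correlations, stabilities and a mediator shift that the documents do not give. If the Study design adjustment was meant to reach mediation, the excess is small, but the plan should say so.

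This is a change that should be made, for the sake of research question 3. The conclusions on programme efficacy do not depend on it.

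**What to change.** In every PROCESS model, add the T0 value of the mediator and the T0 value of the outcome as covariates, alongside sex, age and frailty score. State that raw follow-up scores are used and at which visit mediator and outcome are taken. State whether the baseline-score adjustment in Study design applies to mediation, so that the two passages agree. Confirm that the mediator scales are given at T0, since Table 1 has no schedule of instruments by visit.

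A model with the mediator at T1 and the outcome at T2 would give a better time order, but it needs T2 data in all arms. The plan is unclear on this: Implementation and assessment says "A 6-month follow up (T2) is offered as a booster and final assessment for arms 1 and 2", while Study design schedules T2 without restriction and the recruitment text refers to "participants in Arm 3 who will not receive MBI nor psychoeducation before T2". Reconcile these passages before adopting such a model.

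The bias-corrected bootstrap interval can stay. Requiring significant a and b already holds the per-test error near 5% once both T0 values are in.

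The cost is two covariates per model and a few clarifying sentences. If the mediator scales are in the T0 battery, no new data are needed, and the sample size does not change.
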